For the analysis of routinely collected measures, the primary outcome concerns the test of the average of measures prior to the implementation of the intervention compared with the average of the measures after the implementation of the intervention. Using six steps in the stepped wedge design, the detectable standardized effect associated with the introduction of the intervention (the primary hypothesis) was computed as a function of the *final* sample size within each unit (columns) and the intra-cluster correlation (rows) shown in Table 7⁷⁷. All conditions specified have the ability to detect a medium or smaller effect ($< .50$). The smallest *final* sample size of N=10 provides sufficient power to detect an effect of 0.60 or smaller. Referring to Table 5, we see that all combinations of consent rate and attrition rate yield a *final* sample size of 10 or larger. Based on the results of Tables 7 and 5, the analyses for the routinely collected measures will have sufficient power to detect a clinically meaningful effect (i.e., a standardized effect of .60 or smaller).

Threats to Internal Validity: If outcomes improve with SLUMBER, we will consider explanations alternative to the treatment effect. While unlikely, residents may improve over time unrelated to the SLUMBER intervention. Use of routinely collected measures (MDS) will be investigated to identify possible improvements prior to the introduction of the intervention. MDS measures will also counterbalance the influence that the act of measuring has on the outcome since these measures are collected within routine care. Individuals with poorer outcomes might withdraw due to refusal, discharge or death, thereby creating an illusion of improvement. We will test for systematic attrition by comparing baseline scores of those who withdraw to those who remain. The stepped wedge design staggers introduction of the intervention to mitigate this threat. Spillover training and effects from one unit to the next unit in the same facility not yet engaged are also possible. We will include “manipulation checks” measuring intended changes between units (e.g., noise reductions) to assess whether contamination of sleep strategies occurred in the second unit at a facility before introducing SLUMBER to that unit.

C7. Data Storage and Confidentiality

Data management and quality control are achieved through our electronic data capture and immediately downloaded survey data using computer-assisted data interviewing (CATI). We will conduct monthly data quality checks examining for missing data and out-of-range variable output.

The study PI ([name]) will conduct periodic data quality checks for data storage security and will conduct weekly reviews with the RA and study coordinator to identify potential issues with subject consent and assessment procedures. The New York University Langone Medical Center (NYULMC) Clinical Research Data Management Core (DataCore) will conduct the data management and data quality assurance activities for the SLUMBER study. DataCore personnel have been providing data management support for a combined 50-60 FDA-regulated phase 1 to 4 randomized clinical trials as well as numerous investigator-initiated and National Institute of Health (NIH) funded studies. The primary objectives of the DataCore data management

SLUMBER Protocol V.8/27/2018

methodology are to ensure the completeness and integrity of all study data. To accomplish these objectives, DataCore will provide a comprehensive data management methodology combined with planning, control, and coordination with site staff.

DataCore will develop study Case Report Forms (CRFs) in collaboration with the principal investigator, to standardize collection of survey data. A comprehensive web-based electronic data capture (EDC) system (e.g., REDCap) will be programmed to process, edit and store study data in a centralized database within NYULMC. Each clinical site will enter de-identified data from their corresponding participants directly into the EDC and will not be able to access data from the other sites. DataCore personnel will implement rigorous data validation checks using the EDC system to ensure the highest possible level of data accuracy. The EDC System will be implemented under the spirit of CFR-21 part 11 compliance, with built-in electronic audit trail that maintains a permanent record of all additions, modifications, and deletions of data throughout the life of the study. The system is in compliance with the primary regulatory organizations governing the handling of clinical research study data and is compliant with Food and Drug Administration data systems requirements.

Additional data from the sites (e.g., actigraphy) will be transferred directly to DataCore using a managed file transfer (MFT) platform from Globalscape. The MFT has been implemented at NYULMC to provide enterprise-level security for inter-site collaboration, with built-in regulatory compliance and governance to ensure data safety. DataCore will merge these multiple data streams using unique study participant identifiers and will provide regular backups onto a secure server. This secure server utilizes state-of-the-art firewalls and data encryption services. Moreover, these data are stored without identifying data. A linking file is kept in a separate secure electronic location and contains only data linking information but no other study or clinical data. All data that is transferred to DataCore will remain in the NYULMC datacenter. [name] from UCLA will access the data using a remote desktop connection into NYULMC's Virtual Desktop Infrastructure (VDI). The VDI will be configured so that all analyses and derivative datasets performed by [name] will remain within the NYULMC datacenter. No UCLA individuals will have access to identifiable PHI of study participants.

NYULMC's state-of-the-art high-availability, high-performance offsite datacenter uses a network design based on Cisco Systems' Nexus data center switches. Converged network architecture is optimized for virtualization and uses multiple zones to facilitate a multi-layered environment for additional redundancy and scalability. The data center network provides 10Gbit/sec connectivity to servers and to users in the main campus. Data security is integrated into the network design by segmenting web tier, application tier, and database tier

servers. A next generation firewall system from Palo Alto Networks enables access control based on applications and user profiles; this granular, flexible security policy engine simultaneously enables better services and better security.

C8. Project Management Plan and Timeline (Table 8)

Our research team has been meeting regularly for 18 months and has been in close communication for the past year. We will continue to hold virtual weekly meetings

throughout the study period and additional face-to-face meetings linked to New York trips by Drs. [name] and [name] to conduct SLUMBER trainings. We already use conference call systems, Adobe Connect, and video conferencing quite ably to facilitate communication across institutions. Given that data will be captured electronically in real time, we will be able to manage intervention procedures and data quality and to review our progress at weekly meetings. All key research team members will participate in all aspects of the study design, data analyses, manuscript preparation and manual creation for a multi-site dissemination.

D. Risk/Benefit Assessment

Tasks	Year 1				Year 2				Year 3				Year 4			
	Q1	Q2	Q3	Q4												
Hiring																
Facility Leader Meetings	F1				F2				F3							All
Unit mentor meetings	U1	U1	U2	U2	U3	U3	U4	U4	U5	U5	U6	U6				
Equipment purchase, test																
Equipment set up on unit	U1	U2	U3	U4	U5	U6										
Baseline data gathering	U1	U2	U3	U4	U5	U6										
Unit SLUMBER training	U1	U2	U3	U4	U5	U6										
SLUMBER Intervention		U1	U2	U3	U4		U5	U6								
Follow-up data gathering		U1	U2	U3	U4	U5	U6									
Repeat Unit Follow-ups																
Web/MDS Data collection	F1		F2		F3											
Create single dataset																
Analysis																
Develop Program Manual																
Manuscripts																

(Q1=Quarter 1, etc.; F1=Facility 1, etc.; All=Combined Meeting of all facilities; U1=Unit 1, etc.)

D1. Risk

No pharmacological intervention or medical procedures will be used in this study. Rather this study aims to provide mentoring to nursing facility staff to provide sleep improvement procedures, which are consistent with high quality clinical care.

No interview data will be gathered without resident or proxy consent and although the study procedures are minimal risk, some questions may cause anxiety, embarrassment or be emotionally upsetting. The RA and Study coordinator will receive training in minimizing emotional impact or discomfort and will remind residents that they may discontinue participation or skip portions of the assessments that make them uncomfortable at any time. In the event of significant emotional upset, the PI will be notified and will intervene to address any concerns. A wrist actigraph could become uncomfortable to wear and with that complaint or concern, the device will be promptly removed. We have used the shortest possible recording period to minimize this risk.

Subject loss of confidentiality is another potential risk in clinical trials like the one proposed here and with this type of data collection. However, our CATI data and other data collection methods are specifically designed to eliminate risk of such loss as no data are collected with personal identifiers. Linking files are stored separately. All study personnel will complete training in Human Subjects Research and HIPPA training prior to engaging with participants, and we have a strong record of quality assurance and maintained confidentiality from prior projects. (See C7. Data Storage and Confidentiality)

D2. Protection Against Risk

Any resident who refuses participation will not be approached again. Any resident who declines further participation once enrolled can request to discontinue participation and/or to have his/her data removed. Any subject may become upset, annoyed, or fatigued with interview questions, or use of actigraphy and we will stop gathering study data at the point that this occurs, only resuming if and when that subject is ready and willing to proceed. Our experience with these interview procedures, and wrist actigraphy indicates that this is unlikely to occur but we recognize this possibility and will respond as described. Residents can also request at any time that they not be observed (but note that these observations are done in a completely unobtrusive manner, something that we have successfully done in other studies).

The principal investigator (PI) will provide additional risk protection through notifying the nursing facility about any health related issues that appear to be of an urgent or potentially life threatening nature. A process of study monitoring to review any procedural concerns or subject issues will be included at monthly meetings between the research staff and facility leadership.

We will obtain approvals from the NYU Institutional Review Board (Human Subjects Protection Committee) prior to proceeding with any study procedures. We will also request an exemption from the UCLA IRB, since the only study activities carried out at UCLA will be analyses, and an 'Adverse Events' will be reported to the study IRBs and will include any medical event regardless of its relationship to the study intervention.

D3. Potential Benefit to Subjects

Our proposed research study will provide new information that will address our limited understanding of the measurable impacts of improved sleep. Should we be able to demonstrate improved symptoms among those residents who achieve better sleep, a dissemination of this sleep improvement program could lead to improved quality of life for thousands of nursing facility residents who suffer from negative symptoms that are exacerbated by poor sleep.

This study will enable those engaged nursing facilities and their units to employ targeted practices to promote better sleep and those residents who reside on those units may benefit from an environment that is conducive to better sleep. This study poses minimal risk to subjects, since the study does not involve tests or treatments beyond that which they would normally receive as part of their normal care. Therefore, the benefits outlined above likely exceed the risks of participation in this study.

E. Investigator's Qualifications and Experience

The team of mentors will include Drs. [name] (NYU), [name] (UCLA), [name] (UCLA), and [name] (NYU). Drs. [name] and [name] have experience with the methodology for mentored intervention delivery, and [name] has content expertise on training providers from multiple disciplines on sleep improvement. [name] will contribute additional expertise on how to implement interventions into clinical care in nursing. This team of mentors, with complementary expertise, will work closely with the unit staff during the 3-month intervention period. (See also A4. Preliminary Studies)

Personnel include research assistants (RA) who will be trained in the human subjects' procedures of recruitment, consent, and protection of patient health information before participating in any research activities. All personnel have completed their human subjects training and will be thoroughly trained in the research protocol. Drs. [name] (NYU) and [name] (NYU) have submitted their CVs and investigator financial disclosure forms. The UCLA researchers will submit through their respective IRB. The RAs for the NYU site will be added to this study via a modification submission once they are hired.

F. Subject Identification, Recruitment and Consent/Accent

F1. Method of Subject Identification and Recruitment

The unit nurse will approach all unit residents and ask permission for our research assistant (RA) to approach each resident who agrees to that have that discussion. The RA will not approach any resident who has not given permission to the unit nurse.

F2. Process of Consent

Once the potential subject has been approached and approved by the Unit Nurse, the RA will approach the potential subject for consent. The RA will consent the subject verbally. We request a waiver of documentation of consent as we have done successfully for several other studies where there are issues of literacy and capability to consent in writing (e.g., due to arthritis or visual problems). Under these circumstances, consent is best obtained verbally and actually offers the opportunity to assess for capacity, which cannot be done as easily with written consent alone (see Appendix 8 Resident Script). A requirement of written consent would also unfairly discriminate against those who are not literate, have poor vision or have difficulties with fine motor tasks.

The RA will assess the capacity of every potential subject after they have informed the potential subject about the study. The assessment includes questions about study participation expectations, risks and potential benefits, and what they can do if they feel discomfort (see Appendix 9 Evaluation to Sign Consent Form).

Residents who lack capacity will be verbally assented after the surrogate consents (see Appendix 10 Resident Assent). The assent form will be kept secure with the surrogate's consent form.

F3. Subject Capacity

The Research Assistant will assess capacity for all residents, and any resident who lacks capacity (see Appendix 9 Evaluation to Consent) will not be consented but the Research Assistant will provide the facility with the resident's interest in participation but inability to demonstrate capacity in order to contact his/her identified surrogate via an explanatory letter and a self-addressed, stamped postcard, which will be mailed to the surrogate (see Appendix 2 Surrogate Postcard and Appendix 3 Surrogate Verbal Consent) if they otherwise meet inclusion/exclusion criteria. The facility will identify the resident's legally authorized representative. The Research Assistant and/or PI will offer to meet the surrogate in person, but for the convenience of the surrogate, consent may also be obtained over the phone.

Due to the time sensitive nature of the research, any surrogate who does not return the postcard within 10 days from postmark will be called by a Research Assistant. Verbal consent will be obtained via the phone (see Appendix 3). Consent will be for agreement to wear a wrist actigraph, observation, and provide brief interview responses at baseline, post-intervention, and at 3 and 6-month follow-up.

SLUMBER Protocol V.8/27/2018

Our procedure to assess capacity to consent for research has been used in several prior studies. We note that even some patients with moderate levels of cognitive impairment have the capacity to consent and we will use standardized IRB-approved protocols for conducting this capacity assessment.

F4. Subject/Representative Comprehension

Potential subjects will be told that their involvement in the study is completely voluntary and that they can withdraw from the study at any point. For all potential participants, we will assess the individual's ability to provide informed consent using the interview procedures described in this protocol to assess capacity to consent for research. Some subjects may be too hearing impaired to communicate and with their permission, we may ask their proxy to provide informed consent or we may use assistive technologies or devices such as large-scale print materials or pocket hearing amplifiers to facilitate communication.

F7. Documentation of Consent

Once the RA consents either the subject or the surrogate, they will document their discussion. A signed copy of the informed consent (Appendix 11 Informed Consent Form) signed by the RA will be provided to the subject, and a copy will be provided to the surrogate when applicable. A second signed version of the informed consent document will be kept by the PI in a double-locked file cabinet that is accessible only to the PI and study coordinator.

F8. Cost to Subject

There are no costs for participation.

F9. Payment for Participation

Subjects will not be paid for their participation.

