Level 2 (person) $\pi_{0jk}=\beta_{00k}+r_{0jk}$	coded as 1 if the intervention is implemented in the current (or prior) 3-month period; and otherwise coded as 0. IntvQtr will be the number of quarters since the intervention was applied. We will examine the nature of growth in the outcome as a function of IntvQtr and introduce terms to account for non-linearity as needed. The model to be fit, expressed as a 3-level model fits the "jump" in outcome due to the introduction of the intervention (via the coefficient for γ_{100}) as well as the "slope" over time due to the intervention (via the coefficient for γ_{200}). To examine the impact of removing the intervention, we will further consider a model that introduces two additional time varying covariates (not shown): RemInt coded as 1 if the intervention was removed in the current (or prior) 3-month period, and otherwise coded as 0. This accounts for any deterioration in sleep outcomes when the intervention is ended. RemIntQtr is the number of quarters since the intervention was removed, capturing the change in the slope over time. We will examine the nature of growth in the outcome as a function of RemIntQtr and introduce terms to account for non-linearity as well.
$\pi_{1jk}=\beta_{10k}$	
$\pi_{2jk}=\beta_{20k}$	
Level 3 (unit) $\beta_{00k}=\gamma_{000}+u_{000}$	
$\beta_{10k}=\gamma_{100}$	
$\beta_{20k}=\gamma_{200}$	

Table 5: Final Sample Size (per unit) as Function of Consent % and Attrition % from a 40-Subject Unit

	Consent (%)			
Attrition (%)	45%	50%	55%	60%
25%	13	15	16	18
30%	12	14	15	16
35%	11	13	14	15
40%	10	12	13	14

Table 6: Detectable standardized effect as a function of final sample size per unit and ICC size

ICC	Final Sample size (per unit)				
	10	12	14	16	18
0	0.50	0.45	0.42	0.39	.37
0.10	0.58	0.54	0.51	0.48	.47
0.20	0.65	0.60	0.57	0.55	.53
0.30	0.69	0.65	0.62	0.59	.57
0.40	0.75	0.70	0.66	0.63	.60

the number of participants in the unit, 2) the consent rate, and 3) the attrition rate. Using the expected unit size of 40, Table 5 shows the final sample size as a function of consent and the attrition rates. These final sample sizes (per unit) are used in the following power calculations (which assume six units, 80% power, alpha of .05, and 2-tailed tests).

Power Analysis of Scheduled Study Assessments: For the analysis of the scheduled study assessments, the primary analysis will test the average of the outcome at baseline versus post-treatment and 3-months. The

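### The primary MDS hypothesis is a before/after average, but the plan ties it to a launch-quarter jump, never gives the contrast for the average, and sizes it in Table 7 under a different model

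*Combined protocol and SAP*

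**What the plan says.** The routinely collected measures are the PHQ-9, the Pain Assessment Interview, the BIMS and the ADLs (C6, Data Analyses).

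C6, Power Analysis for Routinely Collected Measures, describes the main test in two ways. First: "the primary outcome concerns the test of the average of measures prior to the implementation of the intervention", set against the average afterwards. Next, for Table 7: "Using six steps in the stepped wedge design, the detectable standardized effect associated with the introduction of the intervention (the primary hypothesis").

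C6, Analysis of Routinely Collected Measures, prints a model with an intercept, Intv and IntvQtr, plus random intercepts for resident and unit. Intv is "coded as 1 if the intervention is implemented in the current (or prior) 3-month period; and otherwise coded as 0". The second predictor, IntvQtr, is a count: it "will be the number of quarters since the intervention was applied", and its value in the launch quarter is not given. The coefficient γ₁₀₀ is the jump "in outcome due to the introduction of the intervention", and γ₂₀₀ is the slope "over time due to the intervention". The authors will also "introduce terms to account for non-linearity as needed". The printed model has no calendar-period term.

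Nowhere does the plan say which coefficient, contrast or joint test of γ₁₀₀ and γ₂₀₀ tests the primary hypothesis.

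**The concern.** In a model with a jump and a slope, the jump is the effect at IntvQtr = 0. If that is the launch quarter, it is the quarter in which the 3-month programme is still being delivered. It equals the before/after average only if the benefit is constant from launch. The plan does not assume this: it fits a slope, and A5 justifies the 3-month time point partly by the time effects need to appear.

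One paragraph therefore supports two primary tests, the average and the jump, and they can give different answers on the same data. The choice could be made after the data are seen. The power statement is affected too, because a detectable effect belongs to a particular contrast in a particular model.

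**Working it through.** **Inputs.** From C6: six units, six steps, 80% power, two-sided α of .05, N = 10, 15 or 20 per unit, ICC 0, .20 or .40. Multiplier: 1.960 + 0.842 = 2.802. Assumptions of this check: seven quarterly periods with one unit crossing at each step; Intv stays at 1 after launch; IntvQtr = 0 in the launch quarter; each quarter's residents treated as independent except where stated.

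**1. Reproducing Table 7.** The stepped-wedge variance for one constant effect with period terms is

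Var = I·s²·(s² + T·τ²) / [(I·U − W)·s² + (U² + I·T·U − T·W − I·V)·τ²],

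with I = 6, T = 7, U = 21 exposed unit-quarters, and W = V = 1 + 4 + 9 + 16 + 25 + 36 = 91. Taking the within-unit residual SD as 1, s² = 1/N and τ² = ICC/(1 − ICC). At N = 10 and ICC .20, s² = .10 and τ² = .25:

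- numerator: 6 × .10 × (.10 + 1.75) = 1.11
- denominator: 35 × .10 + (441 + 882 − 637 − 546) × .25 = 3.5 + 35 = 38.5
- Var = .02883, SE = .170, detectable effect = 2.802 × .170 = .476, against .48 stated.

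All nine cells match to two decimals. With total SD set to 1, only the ICC 0 row matches (.425 and .373 at N = 10 for ICC .20 and .40).

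**2. The average from the jump-plus-slope model.** The 21 exposed unit-quarters split into 6, 5, 4, 3, 2 and 1 at IntvQtr 0 to 5, so mean IntvQtr = (5 + 8 + 9 + 8 + 5)/21 = 35/21 = 1.67. The contrast is γ₁₀₀ + 1.67 × γ₂₀₀. Generalised least squares on unit-quarter means, on the SD scale of step 1, gives these detectable effects for N = 10/15/20:

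| ICC | Table 7 | Average, no period terms (as printed) | Average, period terms added | Jump alone, period terms added |
|---|---|---|---|---|
| 0 | .37/.30/.26 | .27/.22/.19 | .38/.31/.27 | .39/.32/.28 |
| .20 | .48/.39/.34 | .32/.26/.22 | .62/.52/.45 | .48/.40/.35 |
| .40 | .48/.39/.34 | .32/.26/.23 | .64/.53/.46 | .49/.40/.35 |

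Table 7 lies close to the last column, the jump. At ICC .20 and .40 it matches neither version of the average.

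**3. Credit for repeated measures.** The printed model has a resident random intercept, which step 2 leaves out. Suppose the same residents are followed throughout and account for 30%, 50% or 70% of within-unit variance (an assumption). With period terms at ICC .20, the average's detectable effect becomes .53, .45 or .36 at N = 10, and .44, .37 or .29 at N = 15. Resident turnover would reduce this gain.

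**4. A benefit that builds.** Assume effects of 0, .2, .4, then .6 SD held from the fourth quarter on, with N = 10 and ICC .20. The true exposed-quarter average is (5 × .2 + 4 × .4 + 6 × .6)/21 = 6.2/21 = .295.

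| Test | Estimate, model as printed | Power, as printed | Power, period terms added |
|---|---|---|---|
| Jump γ₁₀₀ | .04 | 6% | 6% |
| Average contrast | .30 | 75% | 29% |
| Slope γ₂₀₀ | .15 | 86% | 61% |

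**5. Coding of IntvQtr.** If IntvQtr is 1 in the launch quarter, γ₁₀₀ extrapolates to the quarter before launch. Take a linear benefit that is zero in the launch quarter and averages .48, so the slope is .48/1.67 = .29. Then γ₁₀₀ is −.29.

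**The case against.** A reader might infer that a gradual benefit would be missed. The documents do not support that. The plan never says that γ₁₀₀ alone is the primary test, and it fits a slope with non-linear terms if needed. In step 4 the slope has more power than the average contrast under either model. What stands is that nothing makes the slope primary, while the wording of the hypothesis points to the jump.

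A reader might also infer that the statement below Table 7, that every condition can detect an effect under .50, is false. That is not shown. In the model as printed, the average is detectable at about .32 at N = 10, so Table 7 is conservative. The figures of .62 and .52 need period terms that the plan does not print, and they give no credit for resident-level correlation. With that credit, .50 is met at N = 15 in all three cases and at N = 10 once residents explain about half of the within-unit variance. N = 10 is also the least favourable cell of Table 5 (45% consent, 40% attrition).

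Finally, Table 7 is arithmetically sound. It describes the before/after average if the benefit is constant from launch, and at ICC 0 with period terms the difference is trivial (.38 against .37).

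These points limit the consequences. They do not supply the missing contrast, the IntvQtr coding or the model behind Table 7.

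**Conclusion.** The point holds in a limited form and should be settled before analysis. The coefficient whose description matches the primary MDS hypothesis does not estimate the average that the hypothesis names, and the plan gives no contrast that does. Table 7 was sized for a constant step with period terms, not for the planned jump-plus-slope model. At N = 10 and ICC .20, the detectable average runs from about .32 (no period terms) to .62 (period terms, no resident-level credit), with .53 to .36 in between if the same residents are followed, against .48 stated. Under the assumed building benefit, the choice between jump and average in the printed model moves power from about 6% to 75%.

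The size rests on the assumed seven-quarter layout, IntvQtr = 0 at launch, the residual-SD scale that reproduces Table 7, and an illustrative effect pattern with a plateau. The actual quarterly schedule and resident turnover would change the figures. The mismatch itself rests only on the text.

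**What to change.** - State the primary MDS test as γ₁₀₀ + (mean IntvQtr) × γ₂₀₀, with its own standard error, and say how the mean is weighted. If non-linear terms are added, define the contrast as the mean fitted effect over the exposed quarters. Report the jump and the slope as secondary.
- State the value of IntvQtr in the launch quarter.
- State whether calendar-period terms are fitted.
- Recompute Table 7 and the under-.50 statement for this contrast, under the model to be fitted, including the resident random effect and a range for the resident-level correlation.

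The cost is a few sentences and one table, with no new data and no change to the design. The drawback is that the stated detectable effect may become less favourable if period terms are included.
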